10	Observation status	
The number of follow-up examinations will be calculated by observation time point based on the actual status of follow-up examinations at the observation time point.
 
However, the following criteria should be followed for withdrawals.
 
 • In the case of withdrawal due to "inability to contact" the subject shall be assessed by identifying the time point of dropout based on the scheduled date * and observing the subject up to the previous time. 
However, if the contact is conducted at the relevant time point before "contact is not possible" is established, the observation shall be carried out until that time.
 
 • Other withdrawal dates will be the last follow -up date. 
However, "death" shall be specified based on the expected date. In addition, the time point for "other than death" should be specified after considering the range of adoption of the scheduled date.
 
 • Even if there are no dropouts on the questionnaire, if no follow -up is performed twice at 1 year or later, it is considered dropouts, and the date of first unsupervised follow-up (expected date) is considered the final observation (e.g., if 4-year and 5-year observations are not performed, 1460 days are considered the final observation date). 
※Expected date (scope of employment) 1 year: 365 days (365 ± 30 days) 2 years: 730 days (730 ± 30 days) 3 years: 1095 days (1095 ± 30 days) 4 years: 1460 days (1460 ± 30 days) 5 years: 1825 days (1825 ± 30 days)

11	Analysis set by time point	
The following conditions will be added to the observation status to identify the number of patients included in the analysis at each time point:
 
 • Cases in which death, myocardial infarction, or total revascularization occurred will be included in the analysis at all time points.

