Summary statistics (incidence)	
Incidence rates (%), number of events (molecules), number of populations analyzed (denominators) and 95% confidence intervals of frequencies are calculated. However, cases in which the relevant variable is a missing value are also included in the population of the incidence calculation.
 
4.3 Population numbers for antiplatelet therapy and 4.4 adverse events are specified as follows.
 
4.3 Antiplatelet therapy
 
Newly enrolled patients will be included.
 
Pre-procedure: Case of stenting
 
Procedure Day to Discharge Day: Stenting Cases
 
Procedural Day ~ 8 Months Observation Day: 8 Months Analyzed by Case Time Point of Stenting
 
Procedural Day-1 Year Observation Day: 1 Year Analyzed by Time Point of Stent Implantation
 
Procedural Day ~ 2 Years Observation Day: 2 Years Analyzed by Time Point of Stent Implantation
 
Procedural Day ~ 3 Years Observation Day: 3 Years Analyzed by Time Point of Stent Implantation
 
Procedural Day ~ 4 Years Observation Day: 4 Years Analysis Population by Time Point of Stent Implantation
 
Procedural Day ~ 5 Years Observation Day: 5 Years Analysis Population by Time Point of Stent Implantation
 
4.4 Adverse Events
 
Newly enrolled patients will be included.
 
Procedural Day + 3 Day: Stent Case
 
Procedural Day +4 Days or Beyond to Discharge Day: Stenting Cases
 
The day after discharge to the observation day of Month 8: 8 months for analysis by time point of stenting
 
Observation day of 8 months to 1 year: 1 year for analysis by time point of stenting
 
Observation day 1 to 2 years after the observation day of 1 year: 2 years for analysis by time point of stented patients
 
Observation day of 2-year observation day to 3-year observation day: 3 years for analysis by time point of stented patients
 
Observation day of the following day of observation in Year 3 to Year 4: 4 years for analysis by time point of stent implantation
 
Observation day of the following day of observation in Year 4 to Year 5: 5 years for analysis by time point of stenting
 
During hospitalization: patients with stents
 
Until 8 months: Stent implantation
 
Until 1 year: Stent implantation
 
Until 2 years: Cases of stenting
 
Until 3 years: Cases of stenting
 
Until 4 years: Cases of stenting
 
Until the end of the survey: patients undergoing stent placement
 
Overall post-procedure: stenting cases

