4.1.3. Observation status

Follow-up by booklet and the number of patients included in the analysis by time point will be tabulated.

Table 2. Conduct of follow-up examinations

- Subjects for analysis: Subjects for investigation

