4.4. Adverse Events

4.4.1. Adverse events (composite endpoint)

For adverse events (composite endpoint), incidence rates will be calculated by product for each time of onset.

No	Time of onset
1	Procedural day + 3 days from procedure date
2	Procedural Day + Day 4 or later to discharge date
3	Observation day of the day after discharge to Month 8
4	Observation day of Month 8 to Observation day of Year 1
5	Observation day of 1 year to the following day of 2 years
6	Observation day of the following day of Year 2 to Observation day of Year 3
7	Observation day of Year 3 to Year 4
8	Observation day following the observation day of Year 4 to the observation day of Year 5
9	During hospitalization
10	Up to 8 months
11	Until one year
12	Until 2 years
13	Up to 3 years
14	Up to 4 years
15	Until the end of the survey
16	Entire post-procedure

Table 18. Adverse events (composite endpoint, by time of onset)

- Analysis set: Stent implantation cases (newly enrolled patients)

Items [] indicating Breakdown

No	Item name
1	Target Lesion Failure [TLR Based on Cardiac Death, Myocardial Infarction Associated with Target Vessels, and Ischemic Findings].
2	Death + myocardial infarction + revascularization [death, myocardial infarction, revascularization]
3	Target vessel failure [cardiac death, myocardial infarction, TLR based on ischemic findings, TVR (non-TLR) based on ischemic findings, TVR (TLR or TVR (non-TLR)) based on ischemic findings].
4	Major adverse cardiac events (cardiac death, total myocardial infarction, TLR based on ischemic findings)
5	Death or myocardial infarction
6	Cardiac death or myocardial infarction
7	Myocardial infarction related to cardiac death or target vessel

Determination of myocardial infarction is based on the WHO (SPIRIT III) definitions

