4.4.2. Adverse Events (by Event)

For adverse events (by event), the incidence rate will be calculated by product for each time of onset.

Table 19. Adverse events (by event and time of onset)

- Analysis set: Stent implantation cases (newly enrolled patients)

Items [] indicating Breakdown

No	Item name
1	Death [cardiac death, death attributable to non-coronary vessels, death not attributable to cardiovascular causes]
2	Myocardial infarction [ST-segment elevation myocardial infarction, non-ST-segment elevation myocardial infarction, Q-wave myocardial infarction, non-Q-wave myocardial infarction]
3	TLR [TLR based on ischemic findings [CABG, PCI], TLR not based on ischemic findings [CABG, PCI].
4	TVR (non-TLR) [TVR (non-TLR) [CABG, PCI] based on ischemic findings, TVR (non-TLR) [CABG, PCI] not based on ischemic findings].
5	TVR (TLR or TVR (non-TLR)) [TVR based on ischemic findings (TLR or TVR (non-TLR)) [CABG, PCI]], TVR not based on ischemic findings (TLR or TVR (non-TLR)) [CABG, PCI]].
6	Non-TVR [CABG, PCI]
7	Total revascularization [revascularization based on ischemic findings [CABG, PCI], revascularization not based on ischemic findings [CABG, PCI].
8	Bleeding

Determination of myocardial infarction is based on the WHO (SPIRIT III) definitions

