4.4.4. Adverse events (survival time analysis)

Cumulative incidence is plotted by Kaplan-Meier for the AEs defined below, with the first occurrence as an event and non-occurrence as censored. In addition, the sample size, cumulative incidence, and 95% confidence interval of the cumulative incidence will be calculated for the at-risk population at 240, 365, 730, 1095, 1460, 1825 days, and the entire period.

Figure 21. Adverse events (by survival time analysis event)

- Analysis set: Stent implantation cases (newly enrolled patients)

No	Items	Definitions
1	Event	Death, TLR based on ischemic findings, first occurrence of stent thrombosis as event Use non-event cases as truncation examples
2	Survival time	Event example: Event date-Procedure date + 1 Censored: last contact date or withdrawal date-procedure date + 1

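### SAP definitions 10 and 11 give the later interval rows of Tables 18 and 19 the wrong denominators: patients already dead or lost stay in, some patients at risk drop out, and the net direction depends on rates the documents do not give

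*SAP*

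**What the plan says.** SAP 2.1 builds the time-point sets in two steps. Definition 10 counts a patient at a visit if follow-up at that visit actually took place. From year 1 on, two missed follow-ups make the patient a dropout, dated to the first one missed. Definition 11 then enlarges the set: "The following conditions will be added to the observation status to identify the number of patients included in the analysis at each time point". The only condition listed is "Cases in which death, myocardial infarction, or total revascularization occurred will be included in the analysis at all time points". It has no end at death or at loss to follow-up.

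SAP 3.2 assigns denominators to the adverse event tables of section 4.4 (newly enrolled patients):

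- Separate intervals after discharge use the time-point set at the end of the interval, for example "Observation day of the following day of observation in Year 4 to Year 5: 5 years for analysis by time point of stenting".
- Cumulative rows use all stented patients, for example "Until 4 years: Cases of stenting".

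Both kinds of row appear in Table 18 ("For adverse events (composite endpoint), incidence rates will be calculated by product for each time of onset") and Table 19 ("For adverse events (by event), the incidence rate will be calculated by product for each time of onset"). The antiplatelet rows of Table 17 from month 8 onward use the same time-point sets.

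Two other displays bear on the point. For Table 2, SAP 4.1.3 says: "Follow-up by booklet and the number of patients included in the analysis by time point will be tabulated". SAP 4.4.4 plans Kaplan-Meier curves with numbers at risk, limited to these events: "Death, TLR based on ischemic findings, first occurrence of stent thrombosis as event".

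**The concern.** An interval rate should divide events in the interval by the patients who could have had one and been seen to have it. Definition 11 puts into the year 4-5 denominator everyone who died in years 1 to 4 and everyone lost after an infarction or revascularization in those years. No passage takes them out again. Their number grows with follow-up, which pulls the later interval rates down.

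Definition 10 errs in the opposite direction. A living, event-free patient who is lost during the interval, or who misses only that visit, leaves the denominator although at risk for some or all of the interval. That pushes the rate up.

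At stake is the picture of risk by year. It matters mainly for myocardial infarction, revascularization other than ischemia-driven TLR, bleeding and the composites, because these have no Kaplan-Meier analysis and the interval rows are their only direct display of risk by year.

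**Working it through.** **The plan's own figure.** SAP 1.3 gives a half-width of 4.2% for a 15% MACE rate in 300 patients. Clopper-Pearson for 45/300 is 11.16% to 19.55%; half the width is 4.20%, and 4.20/15 = 28%. It reproduces, and it does not involve definition 11.

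**Inputs.** From the documents: 300 patients (taken as all stented) and the rules above. Assumed, because the documents give none: yearly death d = 2-3%, yearly loss among survivors c = 3-5%, share of patients with a prior infarction or revascularization q = 20-30%, share missing a given visit m = 0, 5 or 10%, and a constant true rate of 2% per year.

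**Formulas.** Start with O(0) = 300 under observation.

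- O(k) = (1 − d)(1 − c) × O(k−1)
- At risk in interval k: R = O(k−1)
- Set as written: W = O(k) − m(1 − q)O(k) + all deaths to year k + q × all lost to year k
- Printed rate = 2% × R/W. Relative understatement = 1 − R/W; a negative value is an overstatement.

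**Years 4-5, d = 2%, c = 3%, q = 20%.** O(4) = 245.0 and O(5) = 232.9. Deaths to year 5 are 27.2. Lost are 300 − 232.9 − 27.2 = 39.9, of whom 20% = 8.0 stay in.

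- m = 0: W = 232.9 + 27.2 + 8.0 = 268.0 after rounding. R/W = 245.0/268.0 = 0.914, printed 1.83%, understated by 8.6%.
- m = 5%: 0.05 × 0.8 × 232.9 = 9.3 drop out, W = 258.7, printed 1.89%, understated by 5.3%.
- m = 10%: 18.6 drop out, W = 249.4, printed 1.96%, understated by 1.8%.

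**Years 4-5, d = 3%, c = 5%, q = 30%.** O(4) = 216.3 and O(5) = 199.3; deaths 38.5; lost 62.2, of whom 18.7 stay in.

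- m = 0: W = 256.5, R/W = 0.843, printed 1.69%, understated by 15.7%.
- m = 5%: W = 249.5, understated by 13.3%.

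**All eight combinations of d, c and q, relative understatement:**

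| Interval | m = 0 | m = 5% | m = 10% |
|---|---|---|---|
| Years 1-2 | −0.7 to +2.0% | −4.6 to −1.2% | −8.9 to −4.7% |
| Years 2-3 | +2.6 to +6.3% | −1.0 to +3.3% | −5.0 to +0.2% |
| Years 3-4 | +5.9 to +11.0% | +2.4 to +8.4% | −1.4 to +5.6% |
| Years 4-5 | +8.6 to +15.7% | +5.3 to +13.3% | +1.8 to +10.8% |
| Years 4-5, d = 1% | +4.5 to +7.5% | +0.8 to +4.6% | −3.1 to +1.5% |

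For m = 0 to 5% and d = 2-3%, a true 2% prints as 1.78-1.95% in years 3-4 and 1.69-1.89% in years 4-5. The two rows between discharge and year 1 were not quantified.

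**Against sampling error.** Five events in 245 give a 95% interval of 0.67-4.70%; five in 268 give 0.61-4.30%. The shift of up to 0.31 points (2.00 − 1.69) lies well inside either.

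**First or all events.** The SAP does not say which the interval rows count. In a simulated cohort (2% death, 2% loss, no missed visits, 20% with an event in year 1 and 3% per year after), the printed-to-true ratios for years 3-4 and 4-5 are 0.93 and 0.90 if all events count. They are about 0.70 and 0.65 if only first events count, because patients who already had the event also remain in the denominator.

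**The case against.** Definition 11 has a sound purpose. A patient who dies within an interval has no visit at its end, so without some such rule the event would be in the numerator and the patient not in the denominator. That stands, and the remedy must keep such patients. It does not justify carrying them into every later interval.

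The consequence is also small. No test, comparator or threshold rests on these rows. Numerators and denominators are printed, Table 2 shows the set sizes and Table 19 shows deaths by interval, so a careful reader could roughly remove earlier deaths. Every endpoint in Tables 18 and 19 has cumulative rows, and death, ischemia-driven TLR and stent thrombosis have Figure 21. All of this stands and is why the point is minor. It discloses the denominator but does not correct the rate.

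A reader might infer that every interval from year 2 on is understated, or that a constant risk must appear to fall. The documents do not support either. With d = 2%, c = 3%, q = 20% and missed visits rising from 0 to 5 to 10% over years 1-2, 2-3 and 3-4, R/W is 285.2/286.2, 271.1/269.6 and 257.7/254.2. A constant 2% then prints as 1.99%, 2.01% and 2.03%. In the other direction, the protocol (section 3) allows telephone contact from year 1 and SAP 3.2 can accept visits outside the window, so missed visits may be few. Neither document gives a figure.

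A reader might also infer that the headline safety results are biased by definition 11. They are not: the cumulative rows, including one-year MACE, divide by all stented patients.

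**Conclusion.** The concern holds as a minor one. The interval denominators of Tables 18 and 19 include patients who are dead or no longer observed and omit some who are at risk. Either error is enough to make the denominator wrong, and the net direction cannot be read from the documents.

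With 2-3% yearly death, 3-5% yearly loss, a 20-30% prior-event share and 0-5% missed visits, years 3-4 are understated by about 2-11% and years 4-5 by about 5-16% in relative terms. With 10% missed visits the ranges are about −1% to +6% and 2% to 11%. At 1% yearly death, years 4-5 are understated by only about 1-5% with 5% missed visits, and run from −3% to +1.5% with 10%. Years 1-2 and 2-3 have no fixed direction. The absolute shift is at most about 0.3 points on 2%. The figures assume that all events are counted; if only first events are, the shortfall is larger.

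**What to change.** In SAP 3.2, set the denominator of each post-discharge interval row of section 4.4 to newly enrolled stented patients who, before the interval began, had not died, withdrawn or met the dropout rule of definition 10. Say explicitly that a patient who misses a single visit stays in, as does a patient whose event falls within the interval.

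State whether the rows count first events or all events. If first events only, also require freedom from that endpoint at the start of the interval; this needs a separate denominator for each endpoint.

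Alternatively, report person-time or Kaplan-Meier interval rates for infarction, revascularization, bleeding and the composites. These also handle patients lost during the interval, about 7-11 in years 4-5 under the main assumptions. If such patients are observed for half the interval on average and no visits are missed, the current rule prints a true 2% as 1.65-1.80% in years 4-5 and the start-of-interval denominator prints 1.95-1.97%; person-time or Kaplan-Meier removes the rest.

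Check the Table 17 denominators, which use the same sets. The cumulative rows do not use definition 11 and need no change on this account.

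The cost is a short SAP edit and some programming, more if denominators are set per endpoint. No new data are needed. With no missed visits the year 4-5 denominator falls by about 23-40 patients (268.0 to 245.0, and 256.5 to 216.3), so late-interval confidence intervals become slightly wider.

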2.2. Definition of Terms

No	Term	Content
1	Dual antiplatelet therapy	Concomitant use of aspirin and thienopyridines (clopidogrel, ticlopidine)

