4. PATIENT TREATMENT

Patient treatment strategy should be determined by the physicians based on standard PCI procedure at each of the sites. Physicians should review the most updated IFU, and carefully consider contraindications, warnings, and precautions when considering patient treatment.

Although dual antiplatelet management is ultimately determined by physicians, enrolled patients will be encouraged to receive adjunctive antiplatelet therapy consisting of an indefinite duration of aspirin in addition to a required minimum of 12 months of thienopyridine (clopidogrel, ticlopidine, etc.). It is recommended that physicians review the requirements of the most recent thienopyridine IFU before treating patients.

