5. OBSERVATION ITEMS AT EACH TIME POINT

5.1 Baseline Information

1) Patient Basic Information

- Index Procedure Date (Date of Registration)
- Birth year and month
- Implant of XIENCE PRIME STENT (Only basic information, non-implant stent form and device deficiency form must be completed in the case all PRIME stents are failed to implant)
- Gender
- Height
- Weight
- Admission and Discharge dates

2) Cardiac Status at the Index Procedure and Cardiac History

- Cardiac Status (Symptom of ischemia) at the Index Procedure
- History of Myocardial Infarction
- Previous CABG
- Previous PCI

3) Risk Factors

- Family History of Premature Coronary Artery Disease

Confidential and Proprietary

Do not distribute or reproduce without the prior written permission of Abbott Vascular Inc.

- Smoking History
- Hypertension
- Dyslipidemia
- Diabetic Mellitus
- Renal Disease
- History of Stroke
- History of Major Bleeding
- Unstable Arrhythmia
- Chronic Anticoagulant Therapy

4) Pre-Procedure ECG**5) Pre-Procedure Cardiac Enzyme and Creatinine**

- Cardiac Enzyme
 - CK
 - CK-MB (If MI is suspected then must be measured per site standard practice)
- Serum Creatinine

6) Pre-Procedure Antiplatelet

- Aspirin
- Clopidogrel
- Ticlopidine
- Other anti-platelet medications
-

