1.4. Treatment of patients

The treatment plan should follow the standard of care when performing coronary interventions at each center at the discretion of the physician.

Physicians should discuss patient treatment with reference to warnings, contraindications, and PRECAUTIONS included in the updated package insert.

The final decision for antiplatelet therapy will be made by the doctor, but the package insert for the device requires that subjects at low risk of bleeding receive aspirin indefinitely and thienopyridines (e.g., clopidogrel, ticlopidine) for at least 6 months. In addition, XIENCE PIME package insert states that thienopyridines will be administered for at least 12 months to subjects with XIENCE PRIME in place. Refer to the updated version of the thienopyridine package insert before starting treatment for each patient. Laboratory tests and clinical observations necessary to evaluate the adverse reactions of thienopyridines should be conducted in accordance with the package insert.

2. Definition of analysis set and abbreviations

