4.3. Antiplatelet therapy

4.3.1. Antiplatelet therapy

For antiplatelet therapy, the proportion and confidence interval of the relevant cases will be calculated by product for each observation time point.

No	Time of observation
1	Before the procedure
2	Procedure Day to Discharge Day
3	Procedural date-8 months observation day
4	Procedural date-Observation date of Year 1
5	Procedural date-Observation date for 2 years
6	Procedural date-3 Years Observation Day
7	Procedural date-Observation date, Year 4
8	Procedural date-5 Years Observation Day

Table 17. Antiplatelet therapy (by observation time point)

- Analysis set: Stent implantation cases (newly enrolled patients)

Items

No	Item name
1	Dual antiplatelet therapy [aspirin + clopidogrel, aspirin + ticlopidine]
2	Aspirin, clopidogrel, ticlopidine, cilostazol, and others

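### SAP 2.2 and Table 17 name only two thienopyridines in dual antiplatelet therapy, so the reported dual-therapy proportion can be understated relative to the open list in Protocol 4 and SAP 1.4

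*SAP*

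**What the plan says.** Four places describe the thienopyridine component, and they do not agree.

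- **SAP 2.2 (Definition of Terms)** has a single entry, dual antiplatelet therapy: "Concomitant use of aspirin and thienopyridines (clopidogrel, ticlopidine". The parenthesis ends after the second drug, with nothing to mark the two as examples.
- **SAP 4.3.1, Table 17** has the row "Dual antiplatelet therapy [aspirin + clopidogrel, aspirin + ticlopidine". A separate row counts agents one by one: "Aspirin, clopidogrel, ticlopidine, cilostazol, and others".
- **Protocol 4** leaves the class open: "thienopyridine (clopidogrel, ticlopidine, etc".
- **SAP 1.4** also leaves it open: "thienopyridines (e.g., clopidogrel, ticlopidine".

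Other agents can be recorded. Protocol 5.1 lists "Other anti-platelet medications" among the pre-procedure items. Protocol 5.4 collects the type of maintenance antiplatelet drug, its start date and daily dose, and whether it was stopped or continued.

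For the denominators, SAP 3.2 assigns section 4.3 the newly enrolled stented patients for the first two windows and the time-point analysis set for the later ones. It adds that "cases in which the relevant variable is a missing value are also included in the population of the incidence calculation".

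**The concern.** A definition used to tabulate exposure should cover the same regimens as the treatment text it summarises. Here the text admits any thienopyridine, while the definition and its table name two. A patient on aspirin plus a third thienopyridine would appear in Table 17 under aspirin and under others in the single-agent row, and nowhere in the dual-therapy row. The reader could not recover the right figure from the table, because the others category pools every unlisted drug and does not show who also took aspirin.

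Table 17 is the only summary table of antiplatelet exposure that the SAP plans. Protocol 6.1 names stent thrombosis and adverse events caused by antiplatelet drugs as the important evaluation items, and the results for both will be read against it. An understated dual-therapy proportion would give those results the wrong background, even though it does not alter them.

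**Working it through.** **1. The plan's own figure.** The documents give no dual-therapy rate, so there is none to reproduce. The only design figure is the half-width of 4.2% for a MACE rate of 15% in 300 patients (Protocol 2.3, SAP 1.3). The Clopper-Pearson interval of SAP 3.2 for 45/300 runs from 11.16% to 19.55%. The half-width is (19.55 − 11.16)/2 = 4.20%, and 4.20/15 = 28%, as stated. This confirms the interval method used below. The present point does not bear on the MACE figure.

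**2. Which reading the text supports.** Taken alone, the parenthesis in SAP 2.2 could be a set of examples. Two things favour the closed reading: the word that marks examples in SAP 1.4 is absent in 2.2, and Table 17 splits dual therapy into exactly the two named pairs. The next row of the same table does provide for other agents, so the authors expected them but gave them no place within dual therapy.

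**3. Effect on the proportion.** For one Table 17 window, let N be the denominator, A the number on aspirin plus any thienopyridine, and m the number among A whose only thienopyridine in that window is neither clopidogrel nor ticlopidine.

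- Open list: A/N
- Closed list: (A − m)/N
- Difference: m/N

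The m patients stay in N under the denominator rules of SAP 3.2, so the difference equals their share, point for point.

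**4. Illustration.** Assumptions, none of them from the documents: open-list rates of 90% and 80%, and shares m/N of 1% to 20%. N = 300 is the enrolment target and stands in for the actual denominator. Intervals are exact 95%.

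| Share m/N | m | Closed-list rate if open-list rate is 90% (270/300; 86.0 to 93.2) | Closed-list rate if open-list rate is 80% (240/300; 75.0 to 84.4) |
|---|---|---|---|
| 0% | 0 | 90.0% (86.0 to 93.2) | 80.0% (75.0 to 84.4) |
| 1% | 3 | 89.0% (84.9 to 92.3) | 79.0% (73.9 to 83.5) |
| 5% | 15 | 85.0% (80.4 to 88.8) | 75.0% (69.7 to 79.8) |
| 10% | 30 | 80.0% (75.0 to 84.4) | 70.0% (64.5 to 75.1) |
| 20% | 60 | 70.0% (64.5 to 75.1) | 60.0% (54.2 to 65.6) |

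For example, (270 − 15)/300 = 255/300 = 85.0%, which already lies below the lower limit of 86.0% for the open-list rate. The planned intervals describe sampling error only and would not reveal the misclassification.

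**5. Where the effect stops.** Each event analysis was checked for use of dual-therapy status.

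- SAP 4.4.1 and 4.4.2 (composites including MACE, single events including bleeding): incidence by time of onset, no split by antiplatelet therapy.
- SAP 4.4.3 (stent thrombosis): incidence among stented patients, no split.
- SAP 4.4.4 (Kaplan-Meier): no antiplatelet covariate or stratum.
- SAP 4.5.2: 26 background factors. Anticoagulant therapy is among them; antiplatelet therapy is not.

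No planned event result depends on the definition.

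**The case against.** The strongest reply is that no sentence in the SAP says these patients are scored as not on dual therapy. SAP 2.2 leads with the drug class, the text reads like a translation, and a bracketed breakdown need not exhaust its parent row. This stands in part: the closed reading is an inference from the definition, the table and the denominators. But the open reading does not rescue the table. Such patients would then be in the dual-therapy total and in neither listed pair, so the breakdown would not account for the total. Two programmers could follow this SAP and report different rates.

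It can also be said that the size is unknown. That stands. The documents name no third thienopyridine and give no share of users. The Table 17 windows run cumulatively from the procedure day, so a patient who also took a listed drug with aspirin within the window might still count. The share is therefore an upper bound on the understatement.

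A reader might infer more, in two ways that the documents do not support.

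- *That stent thromboses or bleeds would be reported as occurring off dual therapy, distorting both important evaluation items.* No planned output crosses events with dual-therapy status, and Protocol 5.9 has the relationship to antiplatelet therapy judged event by event.
- *That changing drug use over the 2013 to 2019 survey would imitate a fall in dual therapy.* The documents contain nothing on such a change. Registration was targeted to finish by 30 June 2014 (Protocol 3), so if that target held, later drift could not reach the pre-procedure and discharge rows.

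**Conclusion.** The point holds as an inconsistency in how exposure is classified. SAP 2.2 and Table 17 use a two-drug list where Protocol 4 and SAP 1.4 use an open one. Followed as written, the SAP understates the Table 17 dual-therapy proportion by up to the share of patients on aspirin plus another thienopyridine. That share is not in the documents; if it is zero, so is the effect. The conclusion rests on the closed reading, which Table 17 favours but no sentence states, and on such patients having no listed pair within the window.

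The consequence is confined to descriptive proportions to which no test, threshold or decision is attached. It matters because this is the only exposure summary beside the important evaluation items, and because the repair is small. The point concerns how exposure is counted; it takes no view on which drug or duration is right.

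**What to change.** - **SAP 2.2:** define dual antiplatelet therapy, for analysis, as aspirin together with any thienopyridine recorded on the CRF. This brings the definition into line with Protocol 4 and SAP 1.4.
- **Table 17:** add an aspirin-plus-other-thienopyridine line to the dual-therapy breakdown, so that every patient in the total appears in at least one listed combination.
- **Scope:** keep aspirin with a non-thienopyridine agent, such as cilostazol, separate and outside the dual-therapy total. A general aspirin-plus-other line would admit pairs that neither document counts as dual therapy and could overstate the rate.

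The cost is one line of definition, one table line, and a rule assigning recorded drug names to the thienopyridine class. No new data are needed, provided the drug is identifiable in the entries under Protocol 5.1 (other antiplatelet drugs) and 5.4 (type).
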